## 7.6 Disposition of Subjects

The number of all screened subjects will be presented overall. The number and percentage of all subjects enrolled and included in the SAF and PK analyses sets who completed the study and prematurely discontinued the study, who completed study treatment and prematurely discontinued study treatment, study duration and treatment duration (Part 2 only), will be summarised. The number and percentage of subjects will be summarised by their reasons for withdrawal from the study and study treatment.

Study duration will be derived as the number of days between study Day 1 and the date of study completion or the date of early study withdrawal.

Eligibility for each of the analysis sets along with reasons for exclusion will be listed. Inclusion and exclusion criteria will be listed. Study completion/withdrawal data will be listed. Informed consent date and the protocol version enrolled under will also be listed.

## 7.7 **Protocol Deviations**

Prior to database lock, Zambon will provide the individual deviations and their classifications prior to database lock and analysis set assignment.

Details of all important protocol deviations (date, deviation group, deviation category and specific details) will be listed.

## 7.8 Background and Demographic Characteristics

#### 7.8.1 Demography

Demographic characteristics (age, sex, and race), body measurements (height, weight and body mass index (BMI)) collected at Screening and time since diagnosis of asthma (Parts 2 & 3 only) will be summarised. For part 3, asthma severity will also be summarised.

Age is calculated in years on the date of first administration of study treatment.

BMI will be reported using the values entered into the eCRF.

Time since asthma diagnosis is derived using the date of informed consent.

All subject demographic data including informed consent will be listed.

#### 7.8.2 Smoking History

Smoking history data will be listed only.

#### 7.8.3 Medical History

Medical history events (not including asthma diagnosis) will be coded using the latest Medical Dictionary for Regulated Activities (MedDRA) dictionary version. The version used will be indicated in the data summaries and listings. The number and percentage of subjects will be presented for ongoing conditions and previous conditions (stop date prior to screening) separately by system organ class (SOC), and preferred term (PT), where SOC and PT will be presented in decreasing frequency of the total number of subjects with medical history events. Subjects will only be counted once per SOC and PT term. All events will be listed.

## 7.9 **Prior and Concomitant Medications**

Medications will be coded using the latest World Health Organization Drug dictionary (WHO Drug) version. The version used will be indicated in the data summaries and listings.

Prior medications are defined as those taken within 28 days prior to screening. Medications that are ongoing at screening or started after screening will be deemed to be concomitant medications. If medication dates are incomplete and it is not clear whether the medication was concomitant, it will be assumed to be concomitant.

For Part 3, the following rules will be used to define whether a medication is concomitant and which treatment they should be assigned to:

- Concomitant to Period 1 only is defined as medication administered from first administration of study drug for Period 1 and finishing prior to the first administration of study drug for Period 2.
- Concomitant to Period 2 only is defined as starting from first administration of study drug in Period 2.
- A treatment starting before the end of Period 1 and continuing into Period 2 will be reported under both periods.
- If medication dates are incomplete and it is not clear whether the medication was concomitant to a single treatment period, it will be assumed to be concomitant to both periods

The number and percentage of subjects taking concomitant medications will be summarised by medication class and standardised medication name, where medication class and standardised medication name will be presented alphabetically. In summary tables, subjects taking multiple medications in the same medication class or having the same standardised medication recorded multiple times in the study will be counted only once for that specific medication class and standardised medication name.

Prior and concomitant medication data will be listed and flagged accordingly.

## 7.10 Administration of Study Treatment and Exposure

Details of the timings of treatment administration will be listed along with the number of doses of study treatment administered, total exposure, and the number and cause of dose interruptions. This will be listed by treatment period for Part 3 and include the treatment received.

## 7.11 Efficacy Analysis

Not applicable.

## 7.12 Pharmacokinetics

#### 7.12.1 Serum concentrations

Serum concentrations of both voriconazole and N-oxide voriconazole will be summarised over time and listed for those in the PK Concentration set. Mean, SD, minimum, maximum and median will be presented.

Similar analyses will be completed for the PK parameters listed in section 3.2.2 for those subjects in the PK Parameters set. Additionally, the geometric mean, CV% and geometric SD will also be presented.

Mean (±SD) serum concentration profiles will be plotted on the original scale and on the log scale. Samples below limit of quantification (BLQ) prior to the first quantifiable concentration will be set to zero. Samples with concentrations BLQ after the first quantifiable concentration will be set to 'missing' and omitted from the analysis. Other PK parameters will be calculated according to standard equations.

If a value is considered to be anomalous due to being inconsistent with the expected PK profile, it may be appropriate to exclude this point from the PK analysis. However, the exclusion of data must have strong justification and will be documented in the raw data and in the clinical study report. The following conditions for PK parameter inclusion may also be applied:

- AUC0-inf, kel, t1/2, CL/F (exception Part 2, Day 10) and Vz/F to be excluded if the regression does not include at least 3 different time points in the terminal phase (after Cmax, but excluding the concentration at tmax)
- AUC0-inf, CL/F (exception Part 2, Day 10) and Vz/F, t1/2, kel to be excluded if the coefficient of determination, Adjusted R^2 in the regression, is less than 0.8
- AUC0-inf, CL/F and Vz/F is excluded if the %extrapolated area is greater than 20% (exception CL/F and Vz/F in Part 2, Day 10)

Metabolite parent ratios will be estimated for  $C_{max}$  and AUC across all parts of the study.

The following rules will be applied if there are BLQ or missing values (e.g. no result (NR)) in serum concentration data series to be summarised:

- If an embedded BLQ value was set to missing for PK analysis, this value will be excluded from the summary statistics. Other BLQ values will be set to 0.
- NR results will be set to missing.
- If all the values are BLQ, then the arithmetic mean, arithmetic standard deviation (SD), median, min and max will be presented as zero, and the geometric mean and geometric coefficient of variation (CV) will be denoted as NC (not calculable).

The PK parameters will be listed together with the sample collection details for each study Part.

#### 7.12.2 Induced Sputum Concentrations

For subjects in the PK Sputum Concentration set for Parts 2 (Day 7) and 3 (Days 1, 2 and 3 for each treatment period) of the study, induced sputum plug and processed sputum concentrations of voriconazole and n-oxide voriconazole will be listed. Where there is sufficient data, induced sputum plug and processed sputum concentrations and PK parameters of voriconazole and n-oxide voriconazole may be summarised

over time. Mean (±SD) induced sputum concentration profiles may also be plotted on the original scale and on the log scale.

#### 7.12.3 Dose proportionality

Dose proportionality of ZP-059 will be assessed by fitting a power model as follows:

$$log_{10}(y) = \alpha + \beta \ log_{10}(dose)$$

Where  $\alpha$  represents the random subject effects for intercept and dose. A value of 1 for  $\beta$  indicates perfect dose proportionality. Therefore, the estimate of  $\beta$  together with the corresponding 90% confidence interval (CI) will be used to quantify dose proportionality. The increase in concentration over the dose range will be estimated by the ratio of the expected concentration with the highest dose to that of the lowest dose. This will be derived by back-transforming the difference on the log10 scale between the two doses and will be accompanied by its associated 90% confidence interval. If the exposure is dose proportional there should be a fold increase equal to the ratio of highest: lowest dose across the dose range.

If it isn't possible to fit random subject slopes a common fixed effect slope will be fitted.

Dose proportionality will be assessed for each of the following PK endpoints for voriconazole and n-oxide voriconazole separately:

- Cmax
- AUC0-t, where t is 12 hours for Part 1, 24 hours for Part 2 and 96 hours for Part 3.
- AUC0-inf

These will be performed separately for Part 1 and Part 2 at Day 1 and Day 10. This analysis will be performed if 3 or more dose levels are used for the Part.

Dose proportionality will also be assessed using an analysis of variance (ANOVA) method. A mixed effects model will be fitted with fixed effects for dose and random effects for subject. The difference between the dose levels will be presented along with a 90% confidence interval and p-value.

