However, despite promising efficacy in ABPA patients and the improved PK profile, systemic, prolonged use of voriconazole is still associated with a significant number of adverse events and treatment discontinuations, with visual toxicity being one of the main reasons for poor patient tolerability [17]. Development of an inhaled formulation of voriconazole could offer an attractive therapeutic alternative, deprived of the side effects associated with systemic exposure.

ZP-059 (inhaled voriconazole) is an anti-fungal product being developed as a therapeutic for the treatment of ABPA in patients with asthma and cystic fibrosis (CF).

This study will evaluate the safety, tolerability and PK of single and multiple ascending doses of ZP-059 capsules administered as dry powder for inhalation in Part 1 to healthy volunteers (single ascending dose; SAD) and in Part 2 to subjects with mild asthma (multiple ascending dose; MAD), respectively.

In Part 3, the bioavailability of ZP-059 in subjects with mild to moderate stable asthma will be compared to that of oral voriconazole. Part 3 will only start after review of safety data from cohorts 1 to 4 of Part 1 (SAD) have been completed.

Parts 2 and 3 of the study will also explore voriconazole concentrations in induced sputum samples in asthmatic subjects.

As part of the safety and tolerability assessment, this study will investigate the effects of ZP-059 on airway function in both mild and mild to moderate stable asthma subjects.

Population rationale:

ABPA affects both men and women; therefore, a target population of both male and non-pregnant, non-lactating female subjects of childbearing potential (providing they agree to use highly effective contraception) or women of non-childbearing potential between 18 and 60 years will be suitable for all parts of the study (i.e. Parts 1, 2 and 3). As PK of voriconazole has been shown to differ between males and females, in all parts of the study (i.e. Parts 1, 2 and 3) every effort will be made to include as close as possible an equal balance between male and female subjects; in Part 1 and Part 2 this will be in each of the individual cohorts.

Japanese and Chinese subjects will not be included in this study as voriconazole exposures in these populations could be influenced by poor metabolism due to CYP2C19 genotype [18].

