4.1. Overall Design

This is an integrated Phase 1, single centre, multi-part, open-label study in both healthy subjects (Part 1), subjects with mild stable asthma (Part 2) and subjects with mild to moderate stable asthma (Part 3). In all parts of the study (i.e. Parts 1, 2 and 3) every effort will be made to include as close as possible an equal balance between male and female subjects; in Part 1 and Part 2 this will be in each of the individual cohorts.

Safety, tolerability and PK will be assessed following either single ascending (SAD) or multiple ascending (MAD) dosing of ZP-059 (Part 1 and Part 2, respectively).

Part 1 will comprise 4 separate cohorts (each containing 6 subjects) planned to receive single doses of ZP-059. The starting dose for Cohort 1 will be 5 mg with subsequent doses being determined from review of safety data by the SAC from the preceding cohorts. The criteria to be followed by the SAC are detailed in Section 6.6.4. The study will have an interleaved design.

Part 2 will comprise 3 separate cohorts (each containing 6 subjects) planned to receive daily doses of ZP-059 on Day 1 to 10. Dose levels for Part 2 will be determined from review of safety data by the SAC from Part 1. Part 2 cohort 1 will commence after a review of safety data from Part 1 cohort 2 confirms that it is safe to do so. The criteria to be followed by the SAC are detailed in Section 6.6.4

Part 3 is a 2-period, randomised crossover study in 16 subjects to assess the safety, tolerability and PK of single doses of ZP-059 and single doses of oral voriconazole. Part 3 will comprise of 1 cohort randomised to receive ZP-059 and 200 mg oral voriconazole; across 2 treatment periods with a minimum wash-out period of 96 hours.

The dose of ZP-059 for Part 3 will be confirmed after completion of SAD cohorts 1 to 4 and review of the available safety data. Hence, dosing of Part 3 may occur prior to/in parallel with dosing in Part 2.

Subjects will be screened for eligibility to participate in the study within 28 days before dosing (Day 1) For Part 2 subjects who completed the initial Screening Visit will attend the clinic on Day -4 or Day -3, for a SARS-COV-2 RT-PCR test. This may be performed on the same day as screening if screening is performed within 3 or 4 days of dosing. Subjects will then be admitted to the clinic on the evening of Day -1.

Further details of each study part are described in Sections 4.1.1 to 4.1.3.

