9.4.4.1. Dose proportionality

Dose proportionality will be assessed by fitting a power model as follows:

$$log_{10}(y) = \alpha + \beta log_{10}(dose)$$

Where a value of 1 for β indicates perfect dose proportionality. Therefore, the estimate of β together with the corresponding 90% CI will be used to quantify dose proportionality. Dose proportionality will be assessed for each of the primary PK endpoint and will be performed separately for Part 1 and Part 2 at Day 1 and Day 10. This analysis will be performed if 3 or more dose levels are used for the Part.

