#### 7.12.4 Bioavailability

The PK endpoints (see Section 7.12.3) estimated from Part 3 of the study will be analysed to assess relative bioavailability of Inhaled Voriconazole (ZP-059) to Oral Voriconazole (VFEND®) by fitting a mixed effects analysis of variance (ANOVA) model to the loge transformed PK parameter including fixed effect terms for treatment, period, sequence and sex and a random effect term for subject (nested within sequence). The adjusted geometric mean ratio (GMR) (Inhaled: Oral) and the corresponding 90% confidence interval (CI) for the adjusted GMR will be presented.

In addition, the PK endpoints will be compared between asthma subjects in Part 3 and healthy subjects in Part 1 and separately with asthma subjects in Part 2 to assess relative bioavailability of the Inhaled Voriconazole (ZP-059) dose taken in Part 3 in these populations. An ANOVA model will be fitted to the loge transformed PK

parameter including terms for the population group (i.e., healthy subjects or asthma subjects) and sex. The adjusted GMR and 90% CI for the adjusted GMR for the comparison between the two populations for the relevant dose will be provided, where the ratio is defined as either Part 3 subjects/Part 1 subjects or Part 3/Part 2 subjects, depending on the comparison.

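### Both dose-proportionality models in SAP 7.12.3 leave out sex, which the protocol says affects voriconazole PK and which both SAP 7.12.4 models include; adding it is a minor, cheap improvement

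*SAP*

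**What the plan says.** SAP 7.12.3 begins "Dose proportionality of ZP-059 will be assessed by fitting a power model as follows" and regresses log exposure on log dose. The slope with its "corresponding 90% confidence interval (CI) will be used to quantify dose proportionality", and the fitted ratio of highest to lowest dose is reported as well. A second analysis follows: "A mixed effects model will be fitted with fixed effects for dose and random effects for subject". Neither lists sex. Protocol 9.4.4.1 has the same power model, also without sex ("Dose proportionality will be assessed by fitting a power model as follows").

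Protocol 2.1 gives the reason for seeking sex balance: "As PK of voriconazole has been shown to differ between males and females". Protocol 4.1 makes near-equal numbers of men and women an aim, and "in Part 1 and Part 2 this will be in each of the individual cohorts". It is a best-effort aim with no quota. Parts 1 and 2 are not randomised (protocol 6.3.1).

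SAP 7.12.4 treats sex differently. The Part 3 crossover model has sex as a fixed effect, and the between-Part ANOVA is fitted to the log "parameter including terms for the population group (i.e., healthy subjects or asthma subjects) and sex". Neither document explains why sex is in these two models and not in the two in 7.12.3.

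**The concern.** In Parts 1 and 2 each subject receives one dose level, so every dose comparison is between subjects. With 6 per cohort, and as few as 4 evaluable (protocol 9.2), a factor that the protocol itself names as a source of PK difference can act in two ways. If the share of women rises or falls with dose, part of the sex difference is read as a dose effect. If the cohorts are balanced, the sex difference goes into the residual and widens the interval.

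The slope, its 90% CI and the high:low ratio are what this analysis delivers, so both effects bear on reported results. The omission also sits oddly. In the crossover, each subject is his or her own control, and with complete data a sex term hardly alters the treatment contrast. The SAP includes sex there and omits it where dose is wholly between subjects.

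**Working it through.** The plan states no precision, sex effect or PK variability for this analysis, so there is no figure to reproduce.

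**Inputs from the documents.** Part 1: 4 cohorts of 6 (24 subjects). Part 2: 3 cohorts of 6 (18). Start 5 mg, single-dose cap 40 mg. 90% CI.

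**Assumptions.** Doses 5/10/20/40 mg in Part 1 and 10/20/40 mg in Part 2. Female:male geometric mean ratio R of 1.2, 1.5 or 2. Residual between-subject CV 40% to 80%. One value per subject per fit, so the fit is least squares on log exposure.

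**1. Shift in the slope.** With x = ln(dose) and z = 1 for a woman, bias = ln R × Sxz / Sxx.

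Part 1: centred x is (−1.5, −0.5, 0.5, 1.5) × ln 2, so Sxx = 6 × 5 × (ln 2)² = 14.41. Females 2, 3, 3, 4 give Sxz = (−3 − 1.5 + 1.5 + 6) × ln 2 = 2.079, and Sxz/Sxx = 0.1443. Females 2, 2, 4, 4 give Sxz = 2.773 and 0.1924. The high:low ratio is multiplied by 8^bias.

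| Part 1 females | R = 1.2 | R = 1.5 | R = 2 |
|---|---|---|---|
| 3, 3, 3, 3 | 0 | 0 | 0 |
| 2, 3, 3, 4: bias (ratio error) | 0.026 (6%) | 0.058 (13%) | 0.100 (23%) |
| 2, 2, 4, 4: bias (ratio error) | 0.035 (8%) | 0.078 (18%) | 0.133 (32%) |

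Part 2, females 2, 3, 4: Sxx = 6 × 2 × (ln 2)² = 5.765 and Sxz = 1.386, so the bias is 0.044, 0.097 and 0.167. Females 4, 2, 4 are imbalanced but have no dose trend: Sxz = 0 and the bias is 0.

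The dose ANOVA compares cohorts directly. A split of 2 women of 6 against 4 of 6 multiplies the ratio of those two cohorts by R^(1/3): 1.06, 1.14 and 1.26.

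**2. Precision under exact 3:3 balance.** SE inflation = √[(s² + 0.25 (ln R)²)/s²], with s² = ln(1 + CV²), which is 0.148 at CV 40% and 0.495 at CV 80%.

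| | R = 1.2 | R = 1.5 | R = 2 |
|---|---|---|---|
| CV 80% | 1.008 | 1.041 | 1.115 |
| CV 40% | 1.028 | 1.130 | 1.345 |

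Allowing for the lost degree of freedom, the adjusted CI becomes the narrower one once R exceeds about 1.04 to 1.10 in Part 1 and 1.06 to 1.13 in Part 2 (CV 30% to 80%).

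**3. Cost of the term.** The 90% t-quantile goes from 1.717 (22 df) to 1.721 (21 df) in Part 1, and from 1.746 (16 df) to 1.753 (15 df) in Part 2. Where sex and dose are correlated, the SE also rises by 1/√(1 − r²), with r² = Sxz²/(Sxx × Szz) and Szz = 24 × 0.25 = 6:

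- 2, 3, 3, 4: r² = 0.05, SE up 2.6%.
- 2, 2, 4, 4: r² = 0.089, SE up 4.8%.
- 1, 2, 4, 5: r² = 0.272, SE up 17%.

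**4. Net effect.** Averaged over all Part 1 splits with 2, 3 or 4 women per cohort, the adjusted slope has a root mean squared error about 1% higher if R = 1, about equal at R = 1.25, 1% to 5% lower at R = 1.5 and 4% to 13% lower at R = 2.

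**The case against.** The strongest reply is that the plan deals with sex by design and that the unadjusted interval is sound. Balance is sought in every cohort of exactly the two parts concerned. If imbalance arises by chance, the sex variance is already in the residual. Simulating the Part 1 design (R 1.2 to 2, CV 40% and 80%), the unadjusted 90% CI covers 0.90 to 0.91 with sex fully random, 0.90 to 0.95 with 2 to 4 women per cohort, and 0.90 to 0.98 with 3:3. So it is valid or conservative. The documents give no reason to expect a systematic drift of sex with dose.

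The scenarios are also selected. If 2, 3 or 4 women per cohort are equally likely, only 2 of the 3⁴ = 81 splits (2.5%) are as extreme as 2, 2, 4, 4 in either direction. For 2, 3, 3, 4 at R = 1.2 to 1.5, the bias of 0.026 to 0.058 compares with a 90% half-width of about 0.18 to 0.33. There is no formal hypothesis test (protocol 9.1) and no acceptance range for the slope, and dose escalation rests on safety data (protocol 6.6).

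Most of this stands, and it lowers the severity. It also rules out two stronger readings. A reader might infer that any sex imbalance biases the slope; only the part that trends with dose does. A reader might infer that the interval is always wider than it needs to be; where imbalance trends strongly with dose, adjustment can widen it (females 1, 2, 4, 5 at R = 1.25: by 11% to 16% for CV 30% to 80%). Nor is the crossover model a strong precedent; the between-Part ANOVA is the real parallel.

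What the reply does not remove is the gain. A conservative interval is one that could be shorter, and valid average coverage does not correct the estimate in a trial whose split happens to trend with dose.

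**Conclusion.** The point holds as a minor one. Sex is absent from both models in SAP 7.12.3, without explanation, although the protocol states a sex difference and SAP 7.12.4 adjusts for it.

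The bias and the loss of precision are largely alternatives: under exact balance the bias is zero and the precision gain is at its greatest, and as the dose trend strengthens the bias grows and the gain shrinks or reverses. All sizes rest on the assumed doses, sex ratios and CVs. The true size is unknown, and the upper figures need a sex ratio of 2, which the documents neither support nor exclude. No decision threshold depends on the result, so the documents do not support calling the dose-proportionality analysis invalid.

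**What to change.** Add sex as a fixed effect to the power model and to the dose ANOVA in SAP 7.12.3, as in 7.12.4. Report the slope, its 90% CI and the high:low ratio from the adjusted model, with the sex split by cohort. That split is best shown for the PK Parameter Set, because SAP 7.5.3 bases the demographic summary on the Enrolled Set. If the team prefers the unadjusted model, the least it should do is prespecify the adjusted one as a sensitivity analysis, or state why sex is left out.

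Sex is already collected (SAP 7.8.1). The cost is one model term and one degree of freedom, about 1% of precision if there is no sex effect, and a somewhat wider CI if sex imbalance turns out to trend strongly with dose.
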